6.2 DURATION OF STUDY PARTICIPATION

6.2.1 Duration of study participation for each patient

The patient will be considered in the study from informed consent signature until death consent withdrawal, or final OS cut-off date, whichever occurs first.

The duration of the study for a patient will include a period for screening of up to 21 days (or up to 28 days for FCBP). A cycle duration is 28 days. Patients will continue study treatment until disease progression, unacceptable AEs, patient wish, or any other reason. All adverse events occurring after informed consent signature will be reported up to 30 days after last study treatment administration.

After study treatment discontinuation, patients will return to the study site 30 days after the last dose of study treatments for end-of-treatment assessments, and 60 days after the last dose of study treatments for assessments including ADA (IPd arm only). If the ADA test at Day 60 is positive or inconclusive, ADA testing will be repeated every 30 days until negative (IPd arm only). If isatuximab is stopped prior to pomalidomide and dexamethasone, ADA will be tested on Day 1 of the 2 next cycles. If the ADA test at the second cycle administered without isatuximab is positive or inconclusive, ADA testing will be repeated every cycle until negative.

The related AEs and all SAEs regardless of relationship to study treatment ongoing at the time of study treatment discontinuation will be followed during the follow-up period until resolution or stabilization. During the follow-up period, any new related adverse events (regardless of seriousness) will be collected and followed until resolution or stabilization.

During FU, patients who discontinue study treatment due to progressive disease (PD) will be followed every 3 months (12 weeks) for further anti-myeloma therapy, second primary malignancies, and survival until death or final OS cut-off date, whichever comes first. Patients who discontinue the study treatment prior to documentation of PD will be followed-up monthly until confirmation of PD (even for patients who would initiate further anti-myeloma therapy without PD), and then every 3 months (12 weeks) for further anti-myeloma therapy, second primary malignancies, and survival, until death or final OS cut-off date, whichever comes first.

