If these criteria are not met on the scheduled Day 1, patients should be re-evaluated weekly. If these criteria are not met within 14 days of the scheduled Day 1 (planned Day 1 Cycle n+1 corresponds to Day 29 Cycle n), the patient should be discontinued from study treatment, unless there is strong evidence of clinical benefit to justify continuation of dosing with study treatment, and the investigator must discuss the rationale with the Sponsor before a decision is taken.

If there are dose modifications within the previous cycle, these guidelines should be followed for the initiation of a new cycle:

- If pomalidomide dosing was halted during the previous cycle and was restarted with a one-level dose reduction without requiring an interruption for the remainder of the cycle, then that reduced dose level will be initiated on Day 1 of the new cycle. Once a dose of pomalidomide or dexamethasone has been reduced, intra-patient re-escalation back to the previous dose level is not permitted.
- Patients may have isatuximab dose omission within a cycle if toxicity occurs and does not recover on the day of planned infusion or within the following 3 days. Within a cycle, a delay of up to 3 days in cases of unresolved toxicity at the time of planned re-administration is permitted, otherwise infusion is omitted. Patients will receive the next isatuximab infusion after recovery of the toxicity as described in [Section 8.2.3.2](#) No dose reduction of isatuximab is permitted.

If one of the study treatments is prematurely permanently discontinued, then other drug(s) can be continued until disease progression or unacceptable toxicity or patient's wish to discontinue of further study treatment. The end of study treatment in this case will be 30 day after the date of the last study treatment administration.

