Adverse event	Recommended action		
	Isatuximab ^a	Dexamethasone ^a	Pomalidomide
			Second episode: same recommendations with decrease of pomalidomide by a second dose level third episode, discontinue pomalidomide
Febrile neutropenia and/or neutropenic infection	
Day 1 of cycle: delay Day 1 administration until fever and infection recover and add G-CSF until ANC > 1 x 10⁹/L^c Then administer Day 1 next cycle with isatuximab and dexamethasone at the same dose level and pomalidomide with dose recommendations below.
 
Within cycle: omit isatuximab and dexamethasone, hold pomalidomide dose and add G-CSF until fever and infection have recovered and ANC > 1 x 10⁹/L. Then administer isatuximab and dexamethasone at the planned days at the same dose level and re-start pomalidomide up planned Day 21 with dose recommendations below:
 
 • first episode, resume same dose pomalidomide with G-CSF or re-start with 1 dose level decrease • second episode, resume with action not done at first episode (same dose with G-CSF or 1 dose decrement pomalidomide) • third episode, resume with one dose decrement of pomalidomide • fourth episode, stop pomalidomide 		

- a Patients may have isatuximab dose omission within a cycle if certain toxicities do not recover within 3 days following the day of planned infusion (see Section 8.2.3)
- b For patients with plasma cells >50% of bone marrow nucleated cells at baseline, to initiate Cycle 2, platelet counts should be ≥30 000/mm³ regardless response status at end of Cycle 1. During Cycles 2-4, platelet counts should be ≥30 000/mm³, if last response is not better than SD, but if last response is PR or better during Cycles 2-4, D1 next cycle can be administered only if platelet counts ≥50 000/mm³. For D1 administration beyond Cycle 4, platelet counts should be ≥50 000/mm³
- c A dose delay of up to 14 days between cycles is permitted in order to recover to the patient's baseline status. Beyond 14 days, the patient must be permanently discontinued from the study (see Section 8.2.3)
- d If G4 neutropenia, assess ANC every 2-3 days until ANC ≥0.5 x 10⁹/L and at least weekly thereafter until ANC ≥1.0 x 10⁹/L

Dose adjustments for patients treated with isatuximab, pomalidomide and dexamethasone combination in the case of non-hematological toxicity are shown in Table 4.

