10.2 DEFINITION OF SOURCE DATA

Source data includes all information in original records and certified copies of original records of clinical findings, observations, or other activities necessary for the reconstruction and evaluation of the trial. Source data are contained in source documents.

Source documents are original documents, data, and records (eg, hospital records, clinical and office charts, laboratory notes, memoranda, patient diaries or evaluation checklists, pharmacy dispensing records, recorded data from automated instruments, copies or transcripts certified after verification as being accurate and complete, microfiches, photographic negatives, microfilm or magnetic media, X-rays, patient files, and records kept at the pharmacy, at the laboratories, and at medical-technical departments) involved in the clinical study. Source documentation must be maintained to support information provided within a CRF.

10.3 HANDLING OF PATIENT PERMANENT TREATMENT DISCONTINUATION AND OF PATIENT STUDY DISCONTINUATION

The study treatment should be continued whenever possible. Study treatment discontinuation should be a last resort. Any study treatment discontinuation should be fully documented in the CRF. In any case, the patient should remain in the study as long as possible.

Patients are free to withdraw their participation at any time during this study. The Investigator has the right to remove any patient from study treatment or participation in the study.

Any study treatment discontinuation should be fully documented in the eCRF.

Pregnancy in patients will lead to definitive treatment discontinuation in all cases.

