10.3.3 Handling of patients after permanent treatment discontinuation

Patients will be followed-up according to the study procedures specified in this protocol up to the scheduled date of study completion, or up to recovery or stabilization of any AE to be followed-up as specified in this protocol, whichever comes last.

If possible, and after the permanent discontinuation of treatment, the patients will complete the evaluations scheduled for the EOT and follow-up visits as detailed in the Study Flow Chart ([Section 1.2](#)).

All treatment discontinuation should be recorded by the Investigator in the appropriate eCRF pages when considered as confirmed.

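### Four dose-table footnotes take patients off the study after a 14-day delay, while Section 8.2.3.1 stops only study treatment and other sections continue follow-up; read literally, toxicity would end endpoint follow-up, now mainly for OS

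*Protocol*

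**What the plan says.** Protocol Table 3 footnote c, Table 4 footnote a, Table 5 footnote c and Table 6 footnote a carry the same rule. A delay of up to 14 days between cycles is allowed; after that, "Beyond 14 days, the patient must be permanently discontinued from the study". Tables 3 and 4 cover the IPd arm and Tables 5 and 6 the Pd arm, for hematologic and non-hematologic toxicity. Each footnote refers the reader to Section 8.2.3.

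Section 8.2.3.1 covers the same situation, restart criteria not met within 14 days of the scheduled Day 1, and says that "the patient should be discontinued from study treatment, unless there is strong evidence of clinical benefit to justify continuation of dosing with study treatment". The investigator must discuss the rationale with the Sponsor first.

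Other sections deal with what happens once treatment has stopped:
- Section 6.2.1: "The patient will be considered in the study from informed consent signature until death consent withdrawal, or final OS cut-off date", whichever is first. It adds: "Patients who discontinue the study treatment prior to documentation of PD will be followed-up monthly until confirmation of PD", and then every 3 months for survival.
- Section 10.3: "In any case, the patient should remain in the study as long as possible".
- Section 10.3.3: "Patients will be followed-up according to the study procedures specified in this protocol up to the scheduled date of study completion", or longer if an adverse event still needs follow-up.

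**The concern.** The same trigger has two instructions that differ in two ways: what ends (the study or study treatment), and whether there is an exception. The cross-reference does not settle this, because it leads to the text that conflicts.

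The first difference bears on the endpoints. If a site closes a patient out of the study, monthly disease assessments and survival contacts stop. Under Protocol 11.4.2.1, PFS is then censored at the last valid assessment. Under SAP 2.1.3.2.1, OS is censored at the last date known alive. The cause of that censoring is slow recovery from toxicity, which is plausibly related to prognosis, so the log-rank and Cox analyses could not safely treat it as non-informative.

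No planned analysis is aimed at this. The five PFS sensitivity analyses in SAP 2.4.4.1.1 vary the assessor, the handling of further therapy, symptomatic deterioration and assessment timing. The optional weighted OS analysis in SAP 2.4.4.2 addresses a switch to subsequent therapy.

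**Working it through.** **1. The rules side by side**

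| Place | Trigger | What ends | Force | Exception |
|---|---|---|---|---|
| Footnotes, Tables 3-6 | Delay beyond 14 days | The study | Must | None |
| 8.2.3.1 | Day 1 criteria not met within 14 days | Study treatment | Should | Strong evidence of benefit, after discussion with the Sponsor |
| 6.2.1, 10.3, 10.3.3 | Treatment stopped | Treatment only; follow-up continues | - | - |

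Section 6.2.1 lists the ways out of the study as death, consent withdrawal and the final OS cut-off. A dose delay is not among them, so the footnotes conflict with 6.2.1 as well as with 8.2.3.1.

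**2. The plan's own figures (Protocol 11.1)**

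PFS events = 4(z0.975 + z0.90)² / (ln 0.60)² = 4(1.960 + 1.282)² / 0.2609 = 161.1, rounded up to 162, as stated.

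OS power at 220 deaths and HR 0.685 is 80.1% with a single look. With O'Brien-Fleming-type spending and looks at 80, 198 and 220 deaths it is 79.2%, against the stated 79.3%. The nominal levels at the second and final looks come out at 0.0181 and 0.0200, as stated. These targets are event counts, so the footnotes do not alter nominal power once 220 deaths are reached.

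**3. How many patients (assumed)**

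The documents give no rate of delays beyond 14 days and no allowance for loss. Assume 5-10% of the planned 300:
- 0.05 × 300 = 15 and 0.10 × 300 = 30 patients.
- 220/300 = 73% of all patients must die to reach the final analysis.
- If removed patients contribute no deaths, the required share of the rest is 220/285 = 77% or 220/270 = 81%.

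**4. Delay to the 220th death (assumed model)**

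Take 15 patients per month for 20 months, exponential OS with medians of 13 and 19 months, and a removed fraction d that contributes no deaths. Expected deaths at month T are (1 − d) times the sum over arms of 7.5 × [20 − (e^(−λ(T−20)) − e^(−λT))/λ], with λ = ln 2/median. Setting this to 220 gives:

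| Removed | Month of 220th death | Shift |
|---|---|---|
| 0% | 40.9 | - |
| 5% | 44.5 | about 4 months |
| 10% | 49.4 | about 9 months |

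The model's 40.9 months with no removal does not match the protocol's 51, so only the shifts should be used.

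**5. Possible bias in the OS hazard ratio (illustration)**

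Simulation with one million patients per arm, control median 13 months and 41 months of follow-up. Removed patients leave between months 1 and 6 and have k times the hazard of the others, and the HR is the ratio of deaths per person-time. Every removal rate and every k is an assumption.

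| Removed, IPd / Pd | k | Planned HR | HR with full follow-up | HR observed |
|---|---|---|---|---|
| 5% / 5% | 3 | 0.685 | 0.686 | 0.681 |
| 10% / 5% | 2 | 0.685 | 0.678 | 0.659 |
| 10% / 5% | 2 | 1 | 0.985 | 0.965 |
| 15% / 5% | 3 | 1 | 0.923 | 0.873 |

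With 5% lost in each arm the shift is 0.005 or less. It is about 0.02 when IPd loses twice as many at double the hazard, and 0.05 only in the extreme case. The direction would reverse if Pd lost more.

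**The case against.** The strongest reply is that follow-up is already protected. The footnotes point to Section 8.2.3, whose text speaks of study treatment. Section 8.2.5 also sets a two-week limit and speaks only of holding treatment. The clinical trial summary, flow-chart footnote ff and Sections 9.1 and 10.1.5.2 all require disease assessment to continue until PD in patients who stop without it. Section 10.3.4 asks sites to seek vital status even for patients who fail to return. On this view a word was dropped from the footnotes, and harm needs a site to follow them against many other sections. Most of this stands: study treatment is the probable intent, and some survival data would be recovered. What remains is an unconditional instruction, printed four times, that contradicts the rule it cites.

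A reader might infer that the loss would fall more heavily on IPd, because the protocol reports Grade 3-4 neutropenia of 85.7% with the triplet (Section 4.4.2.2.2) and 48% with Pd (Section 4.3). The documents do not support that. The first figure is laboratory values in 12 of 14 phase 1b patients, and the second is adverse events in a different trial. Neither is a rate of delays beyond 14 days, and Section 4.5.3 reports no increase in febrile neutropenia or neutropenic infection compared with available Pd data.

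**Conclusion.** The contradiction is certain from the text; the harm is conditional on a site reading the footnotes literally. If that happened, patients slow to recover from toxicity would be informatively censored.

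A reader might also infer that primary PFS is still at risk. For this version it is not. SAP 1.6 dates Amendment 6 after the primary analysis, the present protocol is Amendment 07, and Protocol 6.4 ends IRC review at that cut-off. Rewording now cannot change PFS follow-up already completed, so the exposure left is mainly OS, where follow-up runs to 220 deaths.

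Nor do the documents support a claim of lost power, since the OS analysis is event-driven: loss would delay the analysis and could bias the estimate. The size is unknown. The 15-30 patients rest on an assumed 5-10% of 300, the 4-9 month delay on the exponential model above, and any shift in the hazard ratio mainly on an imbalance between arms that the documents do not show. This is a small, real defect that is cheap to remove.

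**What to change.** Reconcile Table 3 footnote c, Table 4 footnote a, Table 5 footnote c and Table 6 footnote a with Section 8.2.3.1 on two points: what is discontinued, and whether the exception applies. The treatment-stopping rule itself is for the sponsor to decide. Whatever is decided, add to each footnote that disease-assessment and survival follow-up continue as in Sections 6.2.1 and 10.3.3.

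The cost is wording in four footnotes, with no change to event targets, boundaries or analyses. As an optional check, the sponsor could list any patients who left the study after a cycle delay of more than 14 days and seek their vital status where consent allows, since new wording cannot recover follow-up already stopped.

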Table 4 - Guidelines for dose adjustments for non-hematologic toxicities - isatuximab/pomalidomide/dexamethasone combination

Adverse event	Recommended action		
	Isatuximab ^c	Dexamethasone ^c	Pomalidomide
DVT/PE			
Grade 3	
Day 1 of cycle: initiate appropriate anticoagulation therapy and when efficient anticoagulation administer cycle at full dose isatuximab and the same dose level of dexamethasone and pomalidomide^a
 
Within cycle: maintain full dose isatuximab and the same dose level of dexamethasone as planned. For pomalidomide:
 
 • first episode: hold pomalidomide, initiate appropriate anticoagulation therapy and restart same dose pomalidomide when efficient anticoagulation • second episode: despite appropriate anticoagulation pomalidomide permanently discontinued 		

Adverse event	Recommended action		
	Isatuximab ^C	Dexamethasone ^C	Pomalidomide
Grade 4	
Day 1 of cycle: delay Day 1 administration until controlled and administer the full dose of isatuximab and the same dose level of dexamethasone^a
 
Within cycle: delay isatuximab and dexamethasone until stabilization and resume without dose reduction at the next planned dates. If delay is >3 days omit isatuximab and dexamethasone until next planned administration
	Day 1 administration until controlled and the same dose level of dexamethasone ^a	Pomalidomide permanently discontinued.
Edema Grade ≥3 (limiting function and unresponsive to therapy or anasarca), excluding infusion associated reaction	Day 1 of cycle or within cycle : maintain full dose isatuximab as planned	Diuretics as needed, and decrease dexamethasone dose by 1 dose level; if edema persists despite above measures, decrease dose another dose level. If symptoms persist despite second reduction, dexamethasone permanently discontinued	Day 1 of cycle or within cycle : maintain full dose pomalidomide as planned
Allergic reaction/hypersensitivity (excluding infusion associated reaction)			
Grade 2	Hold study treatment until < Grade 2, and patient clinically stable; then, resume study treatment at the same dose level ^a		
	For infusion reaction related to isatuximab, refer to Section 10.6.1		
	For allergic reaction related to pomalidomide, refer to site local protocol		
Grade ≥3	Permanent discontinuation of the drug responsible of the allergic reaction.		

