Hyperglycemia ≥ Grade 3	Day 1 of cycle or within cycle: maintain full dose isatuximab as planned	Treatment with insulin or oral hypoglycemic agents as needed. If uncontrolled despite above measures, decrease dose by one dose level until levels are satisfactory	Day 1 of cycle or within cycle: maintain same dose level of pomalidomide as planned
Muscle weakness ≥ Grade 2 (symptomatic and interfering with function +/- daily activities)	Day 1 of cycle or within cycle: maintain full dose isatuximab as planned	Decrease dexamethasone by one dose level. If weakness persists despite above measures decrease dose by one level. if symptoms persist dexamethasone permanently discontinued	Day 1 of cycle or within cycle: maintain same dose level of pomalidomide as planned
Renal dysfunction			
CrCl <30 mL/min (MDRD formula)	Day 1 of cycle: delay Day 1 administration until CrCl returns to ≥30 mL/min ^a Within cycle: hold study treatment until improvement to ≥30 mL/min. Then re-start full dose isatuximab, same dose level of dexamethasone and pomalidomide up to planned Day 21. If delay is >3 days, omit isatuximab and dexamethasone.		

Adverse event	Recommended action		
	Isatuximab ^c	Dexamethasone ^c	Pomalidomide
Any other drug related non-hematologic Grade 3-4 AE	
Day 1 of cycle: delay Day 1 administration until recovery and apply same rules of dose modification than the rules below^a
 
Within cycle:
 
For isatuximab attribution, omit dose if the event has not recovered within 3 days. Resume at full dose when toxicity has improved to Grade 2 or less or to baseline grade. Second episode, isatuximab discontinuation
 
For dexamethasone attribution omit dose if the event has not recovered within 3 days. Resume with 1 dose level decrease when toxicity has resolved to Grade 2 or less or to baseline grade. Second episode, apply new dose reduction. Third episode, dexamethasone discontinuation
 
For pomalidomide attribution, hold dose. Resume with 1 dose level decrease when toxicity has improved to Grade 2 or less or recovered to baseline grade. Second episode, apply new dose reduction. Third episode, pomalidomide discontinuation
		

- a A dose delay of up to 14 days between cycles is permitted in order to recover to the patient's baseline status. Beyond 14 days, the patient must be permanently discontinued from the study (see Section 8.2.3).
- b See Section 10.6.1 for IAR management.

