b For patients with plasma cells $> 50\%$ of bone marrow nucleated cells at baseline, to initiate Cycle 2, platelet counts should be $\geq 30\,000/mm^3$ regardless response status at end of Cycle 1. During Cycles 2-4, platelet counts should be $\geq 30\,000/mm^3$, if last response is not better than SD, but if last response is PR or better during Cycles 2-4, D1 next cycle can be administered only if platelet counts $\geq 50\,000/mm^3$. For D1 administration beyond Cycle 4, platelet counts should be $\geq 50\,000/mm^3$.

c A dose delay of up to 14 days between cycles is permitted in order to recover to the patient's baseline status. Beyond 14 days, the patient must be permanently discontinued from the study (see [Section 8.2.3](#)).

d If G4 neutropenia, assess ANC every 2-3 days until $ANC \geq 0.5 \times 10^9/L$ and at least weekly thereafter until $ANC \geq 1.0 \times 10^9/L$.

Dose adjustments for patients treated with pomalidomide and dexamethasone combination in the case of non-hematological toxicity are shown in [Table 6](#).

Table 6 - Guidelines for dose adjustments for non-hematologic toxicities - pomalidomide/dexamethasone combination

Adverse event	Recommended action	
	Dexamethasone ^b	Pomalidomide
DVT/PE		
Grade 3	
Day 1 of cycle: initiate appropriate anticoagulation therapy and when efficient anticoagulation, administer cycle at the same dose level of dexamethasone and pomalidomide^a
 
Within cycle: Maintain same dose level of dexamethasone as planned. For pomalidomide:
 
 • First episode: hold pomalidomide, initiate appropriate anticoagulation therapy and restart same dose pomalidomide when efficient anticoagulation • Second episode: despite appropriate anticoagulation pomalidomide permanently discontinued 	
Grade 4	
Day 1 of cycle: delay Day 1 administration until stabilization and administer at the same dose level^a
 
Within cycle: delay dexamethasone until stabilization and resume without dose reduction at the next planned dates. If delay is >3 days omit dexamethasone until next planned administration
	Pomalidomide permanently discontinued.

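### Grade 3 DVT/PE rows of Tables 4 and 6: the Day 1 dosing text is not limited to a first episode, and the second-episode pomalidomide stop is written only under the within-cycle text

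*Protocol*

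**What the plan says.** The Grade 3 DVT/PE row appears in Protocol 8.2.3.3, Table 4 (IPd arm) and 8.2.3.4, Table 6 (Pd arm). In each table it has two labelled parts.

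- **Day 1 of cycle.** Table 4: "initiate appropriate anticoagulation therapy and when efficient anticoagulation administer cycle at full dose isatuximab and the same dose level of dexamethasone and pomalidomide". Table 6 has the same lead-in and then "administer cycle at the same dose level of dexamethasone and pomalidomide". Neither mentions an episode number.
- **Within cycle.** Table 4: "maintain full dose isatuximab and the same dose level of dexamethasone as planned. For pomalidomide", followed by two bullets. At a first episode pomalidomide is held, anticoagulation is started, and pomalidomide resumes at the same dose when anticoagulation is efficient. The other bullet reads "second episode: despite appropriate anticoagulation pomalidomide permanently discontinued". Table 6 runs in parallel: "Maintain same dose level of dexamethasone as planned. For pomalidomide", the same first-episode bullet, then "Second episode: despite appropriate anticoagulation pomalidomide permanently discontinued".

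The footnote attached to the Day 1 text concerns only the 14-day limit on delay between cycles.

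**The concern.** The Day 1 text is an affirmative dosing instruction, so a site that follows the labels has an answer on Day 1 and no reason to look at the bullets below. For a second Grade 3 event that answer is the same dose, where the within-cycle bullets would stop the drug. The documents give no reason why the recommendation should depend on the day the event is handled.

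At stake is re-exposure after a recurrent thromboembolic event, a risk that Protocol 8.9.1 attributes to pomalidomide. The sponsor's own view, in the within-cycle bullets, is that a second Grade 3 event should end pomalidomide. On Day 1 that view has to be inferred.

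**Working it through.** No arithmetic beyond a count applies, so the check sets the texts side by side.

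**Step 1. Compare the two parts of the row, for pomalidomide only (Tables 4 and 6 agree).**

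| Episode | Handled on Day 1 | Handled within cycle | Same outcome? |
|---|---|---|---|
| First | Anticoagulate; same dose once efficient | Hold, anticoagulate; same dose once efficient | Yes |
| Second | Literal text: same dose once efficient | Permanent stop | No |

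The conflict is confined to the second episode.

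**Step 2. Look for another rule that carries the stop to Day 1.**

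- 8.2.3.1, conflicting recommendations: the most conservative adjustment applies, but the rule is worded for a patient with several toxicities, and a repeat of one toxicity is a different case.
- 8.2.3.1, starting a new cycle: related events must have recovered to Grade 1 or baseline, or satisfy the dose-modification tables. This leads back to the row in question.
- 8.2.3.1 and 10.3.2, discontinuation: left to the investigator's opinion. A stop is allowed, but a second DVT/PE is not named.
- 8.2.5: reactions of Grade 3 or higher are held and reinstated if medically appropriate. Again a judgement, with no second-episode rule.

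None of these settles the Day 1 case.

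**Step 3. See how comparable rows connect their parts.** The comparison set is every row of Tables 3 to 6 with both a Day 1/within-cycle split and an episode list. The count goes by wording, because position in the extracted tables is not reliable.

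| Row | Tables | Rows | How Day 1 and the episode list are tied |
|---|---|---|---|
| Febrile neutropenia/neutropenic infection | 3, 5 | 2 | Day 1 points to the recommendations below |
| Any other drug-related non-hematologic Grade 3-4 event | 4, 6 | 2 | Day 1 points to the rules below |
| Grade 4 thrombocytopenia | 3, 5 | 2 | Second episode refers back to the same recommendation(s) |
| Grade 4 neutropenia | 3, 5 | 2 | Second episode refers back to the same recommendation(s) |
| Grade 3 DVT/PE | 4, 6 | 2 | Neither |

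Total: 2 + 2 + 2 + 2 + 2 = 10 rows. Day 1 refers downward in words in 2 + 2 = 4, and does not in 10 − 4 = 6. Of those 6, 4 refer back from the episode list, leaving 6 − 4 = 2, which are the two DVT/PE rows.

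The downward links read, for febrile neutropenia in Table 3, "administer Day 1 next cycle with isatuximab and dexamethasone at the same dose level and pomalidomide with dose recommendations below", and for the any-other-event row in Table 4, "delay Day 1 administration until recovery and apply same rules of dose modification than the rules below". Neuropathy is outside the set because it has no Day 1/within-cycle split. Grade 4 DVT/PE is outside it because pomalidomide is stopped outright, with no episode list.

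**The case against.** The strongest reply is that the Day 1 text was never meant for a second event. It tells the site to initiate anticoagulation, and a patient with a recurrence on anticoagulation is past that point. It doses only when anticoagulation is efficient, which is hard to say of a patient who has just had a recurrence on it. Putting the episode list last in the cell is also common in these tables, so a careful reader could apply the bullets to the whole row. This stands in part: it makes the harmful reading possible rather than certain. It does not remove the gap, because the intention still has to be inferred.

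Two stronger readings are tempting and should not be drawn.

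- A reader might infer that the protocol mandates a stop in one place and contradicts it in another. Both tables are titled as guidelines and the column is headed as recommended action, so each part recommends. Investigator judgement under 8.2.3.1 and 8.2.5 also means that re-dosing is not automatic.
- A reader might infer that the DVT/PE rows are unusual because their Day 1 text lacks a downward reference. Six of the 10 comparable rows lack one. What sets the two DVT/PE rows apart is that they have no backward reference either.

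A further fair point is that the phrase about appropriate anticoagulation in the second-episode bullet can be read as describing the episode or as a circumstance of the stop. If it describes the episode, the row is more coherent: an event without anticoagulation is treated and resumed, and one despite anticoagulation leads to a stop. Even so, the stop remains written only under the within-cycle label.

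Finally, the practical reach is small. The text is amendment 07, dated 26-Nov-2020. SAP Table 1 places the preceding amendment after the primary analysis, and the Clinical Trial Summary ends enrollment no later than the PFS analysis. Only patients still on treatment could be affected, and after the final OS cut-off Protocol 10.1.7 leaves their management to local practice. This stands, and it limits the weight of the point.

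**Conclusion.** The point holds as a minor patient-safety wording conflict. In both tables the Day 1 recommendation is not limited to a first episode, the second-episode stop appears only in the within-cycle part, and no other section joins them.

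The number of patients cannot be derived: the documents give no Grade 3 DVT/PE rate, no recurrence rate and no split by the day an event is handled. Only second Grade 3 events handled on Day 1, in patients still receiving pomalidomide, are affected, so few patients are expected.

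The wording is parallel in the two arms, so it gives no ground for inferring unequal treatment of the arms. Endpoint definitions, alpha and power are untouched.

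The conclusion assumes that sites read the row by its labels. Confidence is medium, because the Day 1 wording itself leans toward a first event.

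**What to change.** In the Day 1 part of the Grade 3 DVT/PE row, change only the pomalidomide clause. In Table 4 keep the full-dose isatuximab and same-level dexamethasone text, and in Table 6 keep the same-level dexamethasone text. In both, end with: *and pomalidomide according to the first/second-episode recommendations below*.

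Leave the episode bullets as the sponsor wrote them, so that the edit does not turn appropriate anticoagulation into a condition for the stop. First-episode dosing is unchanged. Nothing is needed for the other drugs, since 8.2.3.1 already lets them continue when one is stopped.

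The cost is one clause in each of two tables, modelled on a cross-reference the protocol already uses in four rows, with no added procedures. Protocol Section 15 requires IRB/IEC approval before an amendment is implemented, and the Clinical Trial Summary expects approximately 150 sites. The change should therefore go into the next amendment and does not justify one of its own.
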